12.2 Accrual Objectives

This will be a two stage design with 14 patients enrolled in the first stage. If at least one patient responds (response defined as clinical benefit), an additional 13 patients will be

enrolled for a total of 27 patients. Expecting that approximately 3 patients will be un-evaluable due unexpected events, a total of 30 patients will be enrolled in the protocol.

All patients who take at least two weeks of study drug and the non-steroidal aromatase inhibitor will be evaluable for toxicity and efficacy. Depending on accrual, patients who stop study therapy within the first two weeks may be replaced.

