Progression: 25% increase or an increase of 10 sq. cm (whichever is smaller) in the sum of products of measurable lesions over smallest sum observed (over baseline if no decrease), OR appearance of any lesion which had disappeared, OR clear worsening of any evaluable disease, OR appearance of any new lesion/site, OR failure to return for evaluation due to deteriorating condition (unless deterioration is clearly unrelated to this cancer). For scan only bone disease, increased uptake does not constitute clear worsening and new lesions are required for progression. Worsening of existing non-evaluable disease does not constitute progression.

Best Response: This will be calculated from the serial evaluation of objective status. For patients with all disease sites assessed every three to six weeks, two objective determinations of CR, will be required for a best response of CR; two of PR or better, but not qualifying for CR, will be required for PR; two of stable or better, but not qualifying as PR or CR, will be required for stable; and patients with objective status of progression on or before the second evaluation (second AFTER the prestudy evaluation) will have a best response of increasing disease.

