12.1 Endpoint Definitions

Primary endpoint:

- The primary endpoint of this study is clinical benefit (including complete response, partial response, and stable disease) of at least 12 weeks.

Secondary endpoint:

- PFS: evaluate progression free survival in patients treated with the combination of pazopanib and a NSAI in this trial
- Safety : adverse events, SAEs

Exploratory endpoints:

- Evaluate the impact of the combination of pazopanib and a NSAI on circulating tumor cells
- Evaluate the change of immune profile with the combination of pazopanib and a NSAI

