12.6 Sample Size

With 30 patients enrolled, we expect 27 for evaluation at 12 weeks. The two-stage design has 80% power to detect clinical benefit (defined as complete or partial response or stable disease) in 20% of patients compared to <5% of patients without this treatment.

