12.7 Replacement Policy

30 patients will be enrolled for a final estimated study sample size of 27. Patients stopping therapy before 2 weeks will be replaced after discussion with the Study Chair.

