The UCSF Coordinating Center provides administration, data management, and organizational support for the participating sites in the conduct of a multicenter clinical trial. The UCSF Coordinating Center will also coordinate, at minimum, quarterly conference calls with the participating sites or more frequently as needed to discuss risk assessment. The following issues will be discussed as appropriate:

- Enrollment information
- Adverse Events (i.e. new adverse events and updates on unresolved adverse events and new safety information)
- Protocol Violations
- Other issues affecting the conduct of the study

Adverse events reporting to the DSMC will include reports from both the UCSF Coordinating Center, as well as the participating sites. The DSMC will be responsible for monitoring all data entered in OnCore® at the UCSF Coordinating Center and the participating sites. The data (i.e. copies of source documents) from the participating sites will be faxed over to the UCSF Coordinating Center prior to the monitoring visits in order for the DSMC to monitor the participating site's compliance with the protocol, patient safety, and to verify data entry.

Review and Oversight Requirements

Adverse Event Monitoring

Adverse Events (AEs) will be recorded on the UCSF Helen Diller Family Comprehensive Cancer Center CTMS database, all grade 3 and above expected and unexpected AEs will be recorded and updated at each visit.

All Grade 3-5 adverse events entered into OnCore® will be reviewed on a monthly basis at the UCSF Site Committee meetings. All clinically significant adverse events must be reported to the UCSF Coordinating Center by the participating sites within **10 business days** of becoming aware of the event or during the next scheduled quarterly conference call, whichever is sooner. The UCSF Site Committee will review and discuss the selected toxicity, the toxicity grade, and the attribution of relationship of the adverse event to the administration of the study drug(s) from the UCSF Coordinating Center and the participating sites.

In addition, all suspected adverse reactions considered “serious” must be entered in OnCore® and reported to the UCSF Coordinating Center within **1 business day**. The suspected adverse reactions considered “serious” will be reviewed and monitored by the Data and Safety Monitoring Committee on an ongoing basis and discussed at the DSMC meeting, which take place every six (6) weeks.

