If the study has an increase of unexpected or expected Adverse Event grade 3 or 4 above the rate reported in the Investigational Brochure or package insert, the increase rate of AEs will be reported by the Study Chair to the UCSF DSMC at the time of Identification. The UCSF DSMC Chair and Study Chair will discuss the finding and proceed with a written course of action. If at any time the Study Chair stops enrollment or stops the study due to safety issues the UCSF DSMC Chair must be notified within 24 business hours via e-mail. The UCSF DSMC must receive a formal letter within 10 business days and the CHR must be notified.

If any of the above action occurs in a multiple-institutional clinical trial coordinated by the UCSF-CCC, the Study Chair will insure that all participating sites are notified.

Data and Safety Monitoring Committee Contacts:

DSMC Chair: [REDACTED]

[REDACTED]

Email [REDACTED]

Box [REDACTED]

DSMC Monitors

[name]

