Appendix III: management of GI toxicity:

Diarrhea

In cancer patients, diarrhea can be debilitating and potentially life threatening, with dehydration, renal insufficiency, and electrolyte imbalances. Pazopanib as a monotherapy has been associated with an increased incidence of diarrhea, which is grade 1 or 2 in the majority with grade 3/4 diarrhea occurring in approximately 4% of subjects. The incidence and severity may increase when administered with other agents known to cause diarrhea.

Early identification and intervention is critical for the optimal management of diarrhea. A subject's baseline bowel pattern should be established so that changes in that pattern can be identified. In addition, subjects should be educated on signs and symptoms of diarrhea with instructions to report any changes in bowel pattern to the physician.

Diarrhea

The NCI [CTCAE Version 4.0](#) criteria for defining diarrhea are provided below.

Toxicity Grade	Diarrhea (includes diarrhea of small bowel or colonic origin and/or ostomy diarrhea)
1	Increase of <4 stools/day over baseline; mild increase in ostomy output compared to baseline
2	Increase of 4-6 stools/day over baseline; IV fluids indicated < 24 h; moderate increase in ostomy output compared to baseline; not interfering with daily living
3	Increase of ≥ 7 stools/day over baseline; incontinence; IV fluids ≥ 24 h; hospitalization; severe increase in ostomy output compared to baseline; interfering with activities of daily living
4	Life threatening consequences (e.g., hemodynamic collapse)
5	Death

Uncomplicated diarrhea is considered mild to moderate and defined as CTCAE Grade 1 to 2 with no complicating signs or symptoms.

Complicated diarrhea is severe and defined as CTCAE Grade 3 or 4 or Grade 1 or 2 with 1 or more of the following signs or symptoms; cramping, nausea/vomiting, \geq Grade 2, decreased performance status, fever, sepsis, neutropenia, frank bleeding, and/or dehydration. If complicated diarrhea goes unrecognized or untreated, it may lead to death.

Experience thus far suggests that, when pazopanib is used as monotherapy, uncomplicated CTCAE Grade 1 or 2 diarrhea may ensue. In rare cases, subjects treated with monotherapy pazopanib may develop debilitating and potentially life-threatening diarrhea with dehydration, renal insufficiency, and electrolyte imbalances. The pathophysiologic mechanism of diarrhea with pazopanib is not known.

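### The two-week evaluability rule covers toxicity as well as efficacy, so it implies that dosed patients who stop early fall outside the safety denominator, and it conflicts with the progression definition for early deterioration

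*Combined protocol and SAP*

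**What the plan says.** **The population rule.** Section 12.2: "All patients who take at least two weeks of study drug and the non-steroidal aromatase inhibitor will be evaluable for toxicity and efficacy". The same section expects about 3 of 30 enrolled patients to be un-evaluable. It makes replacement of patients who stop inside two weeks optional and dependent on accrual. Section 12.7 states replacement as definite, once the Study Chair has been consulted.

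**Safety.** Section 12.1 lists the secondary endpoint as "Safety : adverse events, SAEs" and names no population. No section defines an all-treated or safety set. Event capture is wider: Section 16.1.1 defines a clinical adverse event for any patient treated with study drug, with no minimum exposure. Section 16.2.1 says that "all grade 3 and above expected and unexpected AEs will be recorded and updated at each visit", and Section 16.2.2 requires serious events to be reported whatever their relationship to the drug. Under Review of Adverse Event Rates, Section 16.2.2 requires a report to the monitoring committee if there is "an increase of unexpected or expected Adverse Event grade 3 or 4 above the rate reported" in the brochure or package insert. It states no denominator.

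**Early stopping.** Table 2 in Section 7.0 requires permanent discontinuation of pazopanib for, among others, arterial thrombosis of any grade, grade 3 or 4 hemorrhage, and grade 4 events in its residual category.

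**Progression.** Section 9.1 counts "failure to return for evaluation due to deteriorating condition" as progression, unless the deterioration is clearly unrelated to the cancer.

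**Decision rule.** Section 12.0 sets 14 eligible and evaluable patients in stage 1, at least 1 with clinical benefit to continue, 13 more for a total of 27, and success at 4 or more. Section 12.6: "With 30 patients enrolled, we expect 27 for evaluation at 12 weeks". Section 12.7: "30 patients will be enrolled for a final estimated study sample size of 27".

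**The concern.** A two-week minimum is a common way to define who can be assessed for efficacy. Using it for toxicity is different, because stopping early can be a consequence of toxicity. A patient with a severe event in week 1 who must discontinue under Table 2 would, by implication, leave the toxicity denominator because of that event. Safety of the combination is a secondary objective, and the Section 16.2.2 rate review depends on whichever denominator is used.

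On efficacy, two sections classify the same patient differently. Someone who takes a week of treatment, deteriorates and does not return is a treatment failure under Section 9.1. Under Sections 12.2 and 12.7 that patient can be set aside and replaced. The clinical benefit rate would then leave out some of the clearest failures.

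A smaller gap is that the bar of 4 is derived for 27 patients while 30 are enrolled, and the plan does not say which patients count if 28 to 30 turn out to be evaluable.

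**Working it through.** **1. Reproduce the design.** Inputs from Section 12.0: n1 = 14, continue if at least 1 benefits; N = 27; success if at least 4 benefit; null rate 0.05, target rate 0.20. The exact probability of success at true rate p is

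P(p) = Σ (x = 1 to 14) C(14, x) p^x (1 − p)^(14 − x) × Pr[Bin(13, p) ≥ 4 − x].

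P(0.05) = 0.0422 and P(0.20) = 0.8066. The stated figures (type I error below 5%, power 80%) are confirmed. Enrolment also agrees: 27 / 0.90 = 30.

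**2. Safety denominator.** Assume 30 dosed, of whom 3 stop before two weeks. Let e be the number with a given severe event among the 3, and m the number among the other 27. The evaluable rate is m/27 and the all-dosed rate is (m + e)/30.

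| e | m | Evaluable only | All dosed |
|---|---|---|---|
| 3 | 0 | 0/27 = 0% | 3/30 = 10% |
| 0 | 1 | 1/27 = 3.7% | 1/30 = 3.3% |

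The all-dosed rate is higher whenever e/3 exceeds m/27, which is the likely direction for events that force discontinuation. For other events it can be lower. The counts are assumed; only the allowance of 3 in 30 comes from the plan.

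**3. Clinical benefit estimate.** At the bar, with 3 early stoppers added to the 27 as non-responders, the rate moves from 4/27 = 14.8% to 4/30 = 13.3%. The number with benefit is still 4, so the decision is unchanged.

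**4. Early deterioration, sections side by side.** Section 9.1 gives progression, hence no clinical benefit. Section 12.2 gives less than two weeks of drug, hence by implication not evaluable. Sections 12.2 and 12.7 allow or require replacement. Nothing says which takes precedence.

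If such patients are instead counted within the 27, the effect on power depends on what the 20% target refers to. If it refers to patients who reach two weeks, and a share d of the counted patients fail earlier, the overall rate is 0.20(1 − d):
- d = 5%: rate 0.19, power at 27 is 77.1%.
- d = 10%: rate 0.18, power at 27 is 73.0%.

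If the 20% already includes early failures, power stays at 80.7%. The documents do not give d, and these values are a range for illustration.

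**5. More than 27 evaluable (minor).** Same formula, bar of 4, second stage enlarged:

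| N | Type I error at 5% null | Power at 20% |
|---|---|---|
| 27 | 4.2% | 80.7% |
| 28 | 4.7% | 82.7% |
| 29 | 5.2% | 84.4% |
| 30 | 5.7% | 86.0% |

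At N = 30 the error is 2.9% if the null rate is 4%.

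**The case against.** Section 12.2 gives a sufficient condition: patients with two weeks of treatment are evaluable. It does not say that others are removed from toxicity tables, and replacing a patient is not the same as deleting one. Section 16.1.1 covers every treated patient, so the safety endpoint can be read as all treated. This stands as far as it goes: exclusion is implied, and the sponsor may well intend to tabulate everyone. But the only sentence that says who is evaluable for toxicity points the other way, and no other section supplies a denominator.

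A reader might infer more than the documents support:

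- *That adverse events in early stoppers are lost.* They are not. Sections 16.1.1, 16.2.1 and 16.2.2 capture and review them.
- *That the Section 16.2.2 review would be missed by a known margin.* The review is a prompt to report and discuss, not a formal test. The diarrhea figure in Appendix III is not identified as the brochure or insert rate, so it cannot serve as the comparator.
- *That leaving out early stoppers breaks the 5% error limit.* That would need a null rate of exactly 5% among all treated patients. Section 12.0 describes the reference rate as expected to be below 5% with no additional treatment. With 10% early stopping without benefit, an all-treated null of 4.5% gives 0.045/0.90 = 5.0% among evaluable patients, and the error is again 4.2%.
- *That 27 against 30 undermines the design.* Sections 12.0 and 12.2 both speak of a total of 27, with 30 as an allowance. Even at 30 the excess is 5.7% − 5% = 0.7 points, and only at a null of 5%.

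It is also fair to object that Section 12.2 attributes un-evaluability to unexpected events, and that early progression need not be one. That is a reason to say so in the plan.

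**Conclusion.** The point holds as a gap in the stated analysis set, and it should be fixed. The two-week rule, with the un-evaluable allowance and the replacement clauses, implies that dosed early stoppers are outside the toxicity set. Because severe events force discontinuation, that exclusion would not be neutral. The size cannot be known in advance; the assumed extreme of 0% against 10% shows what 3 patients in 30 can do. The conflict between Sections 9.1 and 12.2 over deterioration within two weeks is real, though the number affected is unknown and probably small. On efficacy, adding the early stoppers to the 27 as non-responders changes the estimate by about 1.5 points at the bar and does not change the decision. The question of which 27 patients count, and the mismatch between optional and definite replacement, are minor.

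**What to change.** 1. **Safety.** Remove toxicity from the two-week rule in Section 12.2. Analyse safety in every patient who takes at least one dose of study drug, and name that set as the denominator for the rate review in Section 16.2.2.

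2. **Efficacy.** Keep the evaluable set for the primary decision, but count progression as defined in Section 9.1 within the first two weeks as a non-response and do not replace that patient. Add a supporting all-treated clinical benefit rate with all early stoppers as non-responders.

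3. **Minor.** Apply the bar of 4 to the first 27 evaluable patients in order of enrolment (the first 14, then the next 13) and report any later patients descriptively. This keeps 4.2% and 80.7%. Raising the bar to 5 at 30 patients is not equivalent: type I error 1.5%, power 73.6%. Replace the two replacement statements in Sections 12.2 and 12.7 with one.

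**Cost.** Wording in Sections 12.0, 12.2, 12.7 and 16.2.2; no extra patients or visits. The reported benefit rate will be slightly less favourable, and safety rates may move either way. Counting early progressions within the 27 costs some power if the 20% target was meant only for patients who reach two weeks. The protocol should therefore state which patients that target describes.

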12.3 Estimated Duration of Study

Enrollment will occur over 18 months.

Follow-up 6-8 months after last subject enrolled

12.4 Data and Safety Monitoring

Review of adverse events and serious adverse events (defined below) will be done at Site Committee meetings at UCSF and during monthly teleconferences with Yale. In addition, toxicity reviews will occur once a month in the Breast Oncology Program Site Committee meetings at UCSF. We will hold enrollment to review the safety data after the 5th patient has been on pazopanib for 2 weeks and resume once the study is deemed to be safe. The Study Chair will notify Yale of the enrollment hold.

The UCSF DSMC will monitor the study at UCSF and the Yale DSMC will monitor the study at Yale. The Data and Safety Monitoring reports from Yale will be audited by the Quality Assurance, Compliance, and Safety Committee (QUACS) as they are generated from the monitoring reports for the Yale Site.

12.5 Analyses Timepoints

After the first 14 patients have completed 12 weeks of treatment.

12 weeks after the last patient has been enrolled.

12.6 Sample Size

With 30 patients enrolled, we expect 27 for evaluation at 12 weeks. The two-stage design has 80% power to detect clinical benefit (defined as complete or partial response or stable disease) in 20% of patients compared to <5% of patients without this treatment.

12.7 Replacement Policy

30 patients will be enrolled for a final estimated study sample size of 27. Patients stopping therapy before 2 weeks will be replaced after discussion with the Study Chair.

13.0 Data Forms & Submission Schedule

Patients will be evaluated in clinic at least once per cycle of treatment. All collected data will be entered into template forms in OnCore within one week of each patient visit.

14.0 Special Instructions

None

15.0 Ethical Aspects

15.1 Regulatory Considerations

This study will be reviewed by the UCSF and the Yale IRBs as described below. At UCSF, the protocol will also be reviewed by the Helen Diller Family Comprehensive Cancer Center Protocol Review Committee prior to IRB submission. In addition, UCSF will file an Investigational New Drug application with the FDA as described below.

Independent Ethics Committees/Institutional Review Board

This protocol and the informed consent will be approved by the Committee on Human Research (CHR) (UCSF's IRB). Once approved, the protocol will be reviewed by the Yale School of Medicine Human Investigation Committee. The Principal Investigator at each site is responsible for keeping the IRB apprised of the progress of the study and of any changes made in the protocol prior to implementation. The Principal Investigator at each site will also keep his/her own IRB informed of any significant adverse reactions and any protocol exceptions or deviations. Records of all study review and approval documents must be kept on file by the Principal Investigator at each site, and copies of IRB documentation from Yale will be forwarded to UCSF. All records are subject to FDA inspection during or after completion of the study. The IRBs will receive notification of the termination of the study.

Protocol and Protocol Amendments

Protocol and protocol amendments will be submitted to and approved by the UCSF Protocol Review committee (PRC), in addition to CHR, prior to implementation at UCSF.

It is the responsibility of the UCSF Study Chair (or designee) to distribute the protocol and the protocol amendments to Yale upon IRB approval at UCSF. The protocol may be distributed via e-mail or private courier with confirmation of receipt.

Upon approval of the protocol or protocol amendment by Yale's IRB, a copy of the approval documentation must be submitted to Study Chair. All protocol amendments are expected to be approved by Yale's IRB within 90 days of receipt.

Documentation of Yale's protocol approvals will be maintained in the correspondence files by the Study Chair or designee, and provided to the UCSF centralized regulatory staff. It is the responsibility of the Study Chair to review these documents to ensure that the participating sites are using the current protocol version.

Prestudy Documentation at Participating Sites

Before the study may be initiated at Yale, the following documentation must be submitted to UCSF:

- Copy of the official IRB approval letter for the protocol and informed consent form
- IRB membership list
- Form FDA 1572, signed and dated by the Principal Investigator.
- Current curricula vitae and medical licenses of the site's Principal Investigator and all sub investigator(s) listed on Form FDA 1572.
- Contact information (email, phone number, address) for the research pharmacist and designated contact person(s) (CRC and/or nurse) assigned to this study.
- CAP and CLIA Laboratory certification and institution lab normal values
- Executed clinical research contract

Investigational New Drug Application (IND)

The Coordinating Center (UCSF) is responsible for the preparation and submission of the Investigational New Drug Application (IND) to the FDA. An electronic file (PDF) of all FDA correspondence concerning the IND will be maintained in OnCore, the UCSF Helen Diller Family Comprehensive Cancer Center Clinical Trial Management System. It is the responsibility of the Study Chair to keep the regulatory staff informed of any communications with FDA that affect the status of the IND.

Coordinating Center Documentation

It is the responsibility of the Study Chair to maintain adequate files documenting the distribution of study documents as well as their receipt (as applicable). The UCSF Helen Diller Family Comprehensive Cancer Center recommends that the Study Chair maintain a correspondence file and log for each segment of distribution (e.g., FDA, drug manufacturer, sub sites, etc.).

- Correspondence file: should contain copies (paper or electronic) of all protocols and protocol amendments, cover letters, amendment outlines (summary of changes), etc., along with distribution documentation and (when available) documentation of receipt.
- Correspondence log: should be a brief list of all documents distributed including the date sent, recipient(s), and (if available) a tracking number and date received.

At a minimum, the Study Chair must keep documentation of when and to whom the protocol and its updates and safety information are distributed.

